1.2 Study Design

1.2.1 Overview

A 26 month, parallel, two group, open-label, real-world, randomized controlled trial design for patients with severe and complex obesity who are referred to a Tier 3 obesity service (including patients who are referred to a Tier 3 service as part of the bariatric surgery pathway). The total duration of participation will be 104 weeks (+/-2 weeks). Figure 1 shows an overview of the study design.

The first 52 weeks of the study (after randomisation) will determine whether using the

[figure not shown]

targeted prescribing pathway in a Tier 3 setting will result in more participants attaining $\geq 15\%$ weight loss compared with standard care. The purpose of the long-term (52-104 weeks) follow-up is to examine whether LIRA 3mg will help the “early and good” responders to maintain weight loss $\geq 15\%$ in comparison with the control group over a longer period of time compared with standard care. Further, budget impact, cost-effectiveness, improvement in obesity-related co-morbidities, complementary aspects of safety, effectiveness, adherence, and treatment satisfaction of both treatment groups will be assessed and compared.

Participants will be randomised in a 2:1 fashion (2 intervention: 1 control) to either 1) the intervention of targeted prescribing pathway (obesity-specialist care plus targeted use of Liraglutide 3.0mg [LIRA 3mg] with pre-specified stopping rules for the medication) plus standard care, or 2) control (standard care). All participants will be analysed in the group to which they are randomised; in particular, participants in the intervention group who stop receiving LIRA 3mg will remain in the intervention group and will continue to receive standard care for the remainder of the study as per the targeted prescribing pathway (albeit, the part of the pathway where LIRA 3mg is not prescribed; see Figure 1).

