Overall hypoglycaemia rate – ADA definition	52, 104	Hypoglycaemia events will be defined as per Appendix 5 for people without

		diabetes and as per the ADA definition in Appendix 5 for people with diabetes. Hypoglycaemia rate will be calculated per participant as total number of hypoglycaemia events divided by the total follow-up time.
Overall hypoglycaemia rate – Novo Nordisk	52, 104	Hypoglycaemia events will be defined as per Appendix 5 for people without diabetes and as per the Novo Nordisk definition in Appendix 5 for people with diabetes. Hypoglycaemia rate will be calculated per participant as total number of hypoglycaemia events divided by the total follow-up time.
AEs	Continual	Defined as in protocol with MEDRA coding used to classify AEs into System Organ Classes
SAEs	52, 104	Defined as in protocol with MEDRA coding used to classify SAEs into System Organ Classes
Rates of severe hypoglycaemia	52, 104	Calculated per participant as total number of severe hypoglycaemia events divided by the total follow-up time, where severe hypoglycaemia is defined as hypoglycaemic episodes requiring the assistance of another person to actively administer carbohydrate, glucagon, or other resuscitative actions (i.e., 'severe hypoglycaemic episodes')
Change in heart rate from baseline (beats per minute)	52, 104	Follow-up heart rate – baseline heart rate
Compliance of patient with the treatment		
Compliant with Tier 3 service (completers)	52, 104	Binary indicator of 1 if participant is compliant, 0 otherwise (defined in study database)
Stopped treatment with LIRA 3mg because of adverse effects	52, 104	Binary indicator of 1 if participant stopped treatment with LIRA 3mg because of adverse effects*, 0 otherwise. Only defined for participants in intervention arm who were currently eligible for LIRA 3mg treatment. * This includes main reason of 'adverse event' or 'unable to tolerate drug'.
The adherence of participants with the LIRA	52, 104	Participants will be defined as treatment compliant if they self-administer at least 70% of planned doses. Binary indicator of 1 if participant is compliant, 0 otherwise.

3mg (monitored through specific questionnaire and return of used pens)		Given the change in visits as a result of COVID-19 to allow face-to-face, this will be defined using the questionnaire answers as detailed in Appendix 7. Only defined for participants in intervention arm who were currently eligible for LIRA 3mg treatment.

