3.3.5 Safety Population

All individuals randomised into the trial will be in the safety population. Individuals randomised to the intervention will be analysed in the intervention arm unless they have not received a dose of LIRA on the prescribed treatment pathway i.e. the protocol deviations and in particular a deviation from randomised treatment group indicates this is the case. Individuals randomised to the control arm will be analysed in the control arm unless they have received a dose of LIRA as part of the prescribed treatment pathway i.e. the protocol deviations and in particular a deviation from randomised treatment group indicates this is the case.

4 General Issues for Statistical Analysis

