5.8 Changes to the Planned Analysis

In the protocol, it stated that most secondary outcomes would be subject to formal statistical testing, with some secondary outcomes (safety, treatment compliance, treatment satisfaction) tabulated only, without statistical testing. However, due to the large number of secondary outcomes, it was decided that more secondary outcomes should be tabulated only to reduce the impact of multiple testing. The following outcomes were the ones for which the approach changed: obesity-related comorbidities, referrals to Tier 4 services, and physical activity.

In the protocol, the majority of the secondary outcomes were listed as absolute values, however the change from baseline will instead be analysed for continuous variables.

In the protocol, it states that ACR will be analysed as a secondary outcome for participants with diabetes. However, ACR was also measured for participants with prediabetes or hypertension and so these have been added to the ACR secondary outcome definition.

In the protocol, it was stated that participants who had bariatric surgery would be excluded from the complete cases, per protocol, and responder populations. However, it is more likely that these individuals will be poor responders and so excluding them could potentially bias the analyses. Therefore, participants who had bariatric surgery during the study period will be only be included at time-points prior to their bariatric surgery. They will be excluded from time-points after their bariatric surgery.

In the protocol, it stated that adjusted proportions or means would be presented by treatment group in the primary and secondary analyses. However, the unadjusted raw values are presented instead.

6 Safety and Adverse events (AEs)

The safety outcomes (including AEs and SAEs) will be summarised overall, by randomisation group, and by whether or not the participant was currently receiving LIRA 3mg treatment using count and percentage. The following information will also be presented:

- Incidence rate (per person-year) of each System Organ Class of AEs by treatment and overall
- Proportion of participants with at least one AE, by System Organ Class type, treatment arm, and overall
- Incidence rate (per person-year) of each expected AE type by treatment and overall
- Proportion of participants with at least one expected AE, by AE type, treatment arm, and overall
- Bar chart of number of AEs per individual, split by treatment

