- A score of 3 or more is sensitive for moderate-severe OSA but is not very specific, there is a high false positive rate.
- A score of 5-8 is far more specific and indicates a high probability of moderate-severe OSA.

12 Appendix 5: Definitions of hypoglycaemia

A hypoglycaemic episode will be defined as treatment emergent if the onset of the episode is on or after the first day of randomised treatment and no later than 14 days after the last day of randomised treatment. Hypoglycaemic events will be defined as nocturnal if the time onset is between 00:01 and 05:59 (both included).

A hypoglycaemic episode form and an Adverse Event (AE) form must be filled in for all hypoglycaemic episodes. Hypoglycaemic episodes requiring the assistance of another person to actively administer carbohydrate, glucagon, or other resuscitative actions (i.e., 'severe hypoglycaemic episodes') will be qualified as an event of special interest.

A different definition of hypoglycaemia will apply for patients with type 2 diabetes and a different definition will apply for patients without diabetes.

Classification of hypoglycaemia for participants with type 2 diabetes

All participants with diabetes will be supplied with a glucose meter and a diabetes diary for recording of hypoglycaemia, symptomatic episodes and routine blood glucose monitoring. Plasma glucose should always be measured from all participants with diabetes when there is the suspicion of a hypoglycaemic episode.

All plasma glucose values ≤ 3.1 mmol/L (56mg/dL), as well as values > 3.1 mmol/L (56mg/dL) when hypoglycaemic symptoms have occurred should be recorded by the participants in the diaries. Hypoglycaemic episodes will be recorded by the participant in his/her diary throughout the trial and must be transcribed into the CRF by the Investigator at each site visit throughout the trial.

Hypoglycaemic episodes will be summarised based on the American Diabetes Association (ADA) classification and Novo Nordisk's definition.

Novo Nordisk definition

In normal physiology, hypoglycaemia symptoms occur at a blood glucose level of approximately < 2.8 mmol/L (50 mg/dL)/plasma glucose level < 3.1 mmol/L (56 mg/dL). Therefore, Novo Nordisk has used this cut-off value to define minor hypoglycaemia.

Minor hypoglycaemic episode is defined as:

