Total Leisure-Time MET-minutes/week = sum of Walking + Moderate + Vigorous MET-minutes/week scores in leisure.

Total Scores for all Walking, Moderate and Vigorous Physical Activities

Total Walking MET-minutes/week = Walking MET-minutes/week (at Work + for Transport + in Leisure)

Total Moderate MET-minutes/week total = Moderate MET-minutes/week (at Work + Yard chores + inside chores + in Leisure time) + Cycling Met-minutes/week for Transport + Vigorous Yard chores MET-minutes/week

Total Vigorous MET-minutes/week = Vigorous MET-minutes/week (at Work + in Leisure)

Note: Cycling MET value and Vigorous garden/yard work MET value fall within the coding range of moderate-intensity activities.

Total Physical Activity Scores

An overall total physical activity MET-minutes/week score can be computed as: Total physical activity MET-minutes/week = sum of Total (Walking + Moderate + Vigorous) METminutes/week scores.

This is equivalent to computing: Total physical activity MET-minutes/week = sum of Total Work + Total Transport + Total Domestic and Garden + Total Leisure-Time MET-minutes/week scores.

As there are no established thresholds for presenting MET-minutes, the IPAQ Research Committee proposes that these data are reported as comparisons of median values and interquartile ranges for different populations.

14 Appendix 7 Definitions for adherence of participants with the LIRA 3mg

Individuals that didn't receive 70% of the doses as determined by the protocol (i.e. in the first 16 weeks or there after whilst continuing to meet the continue rules of the protocolised treatment schedule) will be classed as not adhering with the LIRA 3mg pathway.

Defining days taking LIRA

The number of days taking LIRA will be calculated as the time from first dose dispensed (normally at baseline visit) to the last known date of individuals taking the LIRA. Where individuals are recorded as not completing the trial due to stopping the LIRA, the date of last dose of LIRA in the completion form will be used; if this is not recorded then the date of first visit at which individuals say they are not happy to continue taking LIRA will be used; and where neither of these are recorded the date of the last visit that individuals said they are happy to continue LIRA will be used.

14.1 52 weeks

Individuals will then be assessed for whether they have received 70% as per table below.

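### The SAP's split of safety outcomes by current LIRA 3mg use has no person-time, so no planned table gives event rates per unit of drug exposure

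*SAP*

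**What the plan says.** - **Hypoglycaemia rates.** SAP 2.2.1 derives the overall rate, under both the ADA and the Novo Nordisk definitions, per participant as "total number of hypoglycaemia events divided by the total follow-up time". The severe rate is the "total number of severe hypoglycaemia events divided by the total follow-up time". Template 16.13 shows these rates, and the overall AE and SAE rates, at 52 and 104 weeks for control and intervention only.
- **AE rates.** SAP section 6 lists "Incidence rate (per person-year) of each System Organ Class of AEs by treatment and overall", and the same for expected AE types. It does not say which person-time is used. The columns of template 16.15 are headed Standard, Liraglutide and Overall.
- **Split by current use.** Section 6 also summarises safety outcomes "by whether or not the participant was currently receiving LIRA 3mg treatment using count and percentage". No template in SAP Appendix 9 has columns for this.
- **Safety groups.** SAP 3.3.5 classifies people by ever having had a dose: "Individuals randomised to the intervention will be analysed in the intervention arm unless they have not received a dose of LIRA" on the pathway. Current exposure plays no part.
- **Exposure.** Under SAP 1.2.3.1 and Protocol 6.2, LIRA 3mg stops at week 16, 32 or 52 if the weight-loss target is missed, while follow-up continues to week 104.
- **Dates available.** SAP Appendix 5 calls a hypoglycaemic episode treatment emergent if its onset is on or after the first day and "no later than 14 days after the last day of randomised treatment". SAP Appendix 7 says "The number of days taking LIRA will be calculated as the time from first dose dispensed" to the last known date of taking it, but this serves adherence and the per protocol population only.

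**The concern.** Section 6 recognises that events on and off the drug are of separate interest, yet the summary it plans cannot compare them. All intervention participants are prescribed the drug at the start. Someone stopped at week 16 then has 16 weeks on drug and 88 off, while someone who passes all three rules has 104 on and none off. The same person can count in both categories, so a count or percentage in either one partly reflects how long people spent there.

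The rates that do have a time denominator are by arm, and intervention time mixes on-drug and off-drug periods by design. A reader of the Liraglutide column in template 16.15 could take a pathway rate for a drug rate. Protocol section 4 justifies the stopping rules partly by reduced exposure and fewer side effects in non-responders, and safety is a secondary objective. As planned, no table would describe that rationale in events per year on and off the drug.

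**Working it through.** **The plan's own figures.** The documents state no on-drug share of follow-up and no expected event rate, so there is no safety figure to reproduce. The response values come from the sample-size paragraph (SAP 1.2.4). With 5% against 16%, two-sided 5% alpha, 80% power and 2:1 allocation, I get 96 + 192 = 288 evaluable. Then 288 / 0.75 = 384, against 392 stated (within 3%). The safety point does not depend on this number.

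**Inputs**
- Response at 52 weeks in the intervention group: 16%, likely range 14% to 20% (SAP 1.2.4).
- Responders at 56 weeks in the cited post-hoc analysis: 24.2% of early responders and 1.8% of early non-responders (Protocol section 4).
- Steps between rules: 16 weeks, 16 weeks (16 to 32), 20 weeks (32 to 52), 52 weeks (52 to 104). Protocol 8.4 gives 24 weeks for the step after week 32, where Protocol 6.2 and the SAP give 20. These passages must be reconciled. I use 20 because the next rule falls at week 52.

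**Step 1: share passing week 16 (p16), inferred.** Solve 24.2 × p16 + 1.8 × (1 − p16) = 16:

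p16 = (16 − 1.8) / (24.2 − 1.8) = 14.2 / 22.4 = 0.634.

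**Step 2: share passing week 52 on drug (p52).** 0.242 × 0.634 = 0.153.

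**Step 3: share passing week 32 (p32), assumed.** It cannot be below p52 or above p16, so the range is 0.153 to 0.634.

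**Step 4: mean on-drug weeks.**
- To week 52: 16 + 16 × p16 + 20 × p32
- To week 104: add 52 × p52

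| | p32 = 0.153 | p32 = 0.634 |
|---|---|---|
| To week 52 | 29.2 weeks (56%) | 38.8 weeks (75%) |
| To week 104 | 37.2 weeks (36%) | 46.8 weeks (45%) |

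Setting p52 to 0.16 instead gives 37.5 to 47.1 weeks, the same rounded shares.

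**Step 5: response range of 14% to 20%.** Then p16 runs from 0.545 to 0.813. Repeating steps 2 to 4 gives 34.2 to 55.5 weeks of 104 (33% to 53%) and 27.4 to 45.3 weeks of 52 (53% to 87%).

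**Step 6: dilution.** If the drug-related excess occurs only on drug, the excess per year of total follow-up is the on-drug excess multiplied by the on-drug share f, so the dilution is 1 / f.
- 104 weeks: 104 / 46.8 = 2.2 to 104 / 37.2 = 2.8
- 52 weeks: 52 / 38.8 = 1.3 to 52 / 29.2 = 1.8

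**Illustration.** Assume an on-drug rate ratio of 2 and no effect off drug. The arm-level ratio is 2f + (1 − f) = 1 + f, about 1.36 to 1.45 at 104 weeks and 1.56 to 1.75 at 52 weeks.

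These shares ignore dropout and stopping for side effects. Early stopping of the drug lowers them. Dropout while on drug shortens both on-drug time and follow-up.

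**The case against.** The strongest reply is that the randomised intervention is the pathway, including the time after LIRA 3mg is withdrawn. For that comparison, events over all follow-up by randomised arm is the right harm measure. That stands. A reader might infer that the planned rates are wrong or understate the harm of the pathway, and the documents do not support this.

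Three other stronger readings also fail.
- *Most intervention time is off drug.* This is a projection. It fits the 104-week rates at the planning value, but the upper end of the response range gives 53% on drug. To week 52, most time is projected to be on drug.
- *Every incidence rate uses total follow-up.* That denominator is written for hypoglycaemia only. For AEs and SAEs the person-time is undefined, although the templates point to arms.
- *The treatment-emergent window is ignored, or means last dose plus 14 days.* SAP 2.2.1 refers to Appendix 5 for the event definitions, so the window may limit the numerator; the text does not settle this. It also says randomised treatment, and people off LIRA 3mg remain in their randomised pathway.

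A further objection is that on-drug and off-drug rates are not a randomised comparison. Those still on drug are selected by response, on-drug time is concentrated early, and Protocol 14.10.1 says gastrointestinal effects may be more frequent at the start of treatment. This stands as a limit on interpretation. The split by current use already planned has the same weakness, and it lacks a time base as well.

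**Conclusion.** The point holds as a gap in the plan, not as an error in the by-arm rates. The split by current LIRA 3mg use cannot show risk per unit of exposure, and no template presents it. The person-time behind the AE and SAE rates is undefined. It is also unclear whether hypoglycaemia numerators are limited to treatment-emergent episodes. If they are, events from a limited window could be divided by all follow-up.

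At the planning response, a drug-related excess confined to on-drug time would appear about 2.2- to 2.8-fold smaller in the 104-week arm rate, and 1.3- to 1.8-fold smaller at 52 weeks. For an event with a background rate, the factor applies to the excess and not to the whole rate. The size rests on a week-16 pass rate inferred from a cited post-hoc analysis, an assumed week-32 range, and no dropout or early stopping for side effects. The comparability problem itself needs none of these assumptions.

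**What to change.** 1. Keep the by-arm rates and define the person-time for each of them, including the AE and SAE rates in section 6 and templates 16.13 and 16.15.
2. State whether the Appendix 5 window limits the hypoglycaemia numerator and what its last day means for people taken off LIRA 3mg. If it applies, match the denominator to it.
3. Replace or supplement the count and percentage split with AE, SAE and hypoglycaemia events per on-drug and per off-drug person-year in the intervention arm, beside the control rate, and add a template. Use the Appendix 7 LIRA dates, less the temporary interruptions recorded under Protocol 8.8.5, and the 14-day window if it is adopted.
4. Label the on-drug and off-drug rates as descriptive, for the reasons of selection and timing given above.

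The cost is a few extra tables and a non-randomised comparison that must carry this caveat. The Appendix 7 dates are a first-to-last span with visit-date fallbacks, so on-drug time will be approximate and subtracting interruptions takes some extra programming. No new data collection is needed.

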- An episode with symptoms consistent with hypoglycaemia with confirmation by plasma glucose < 3.1 mmol/L (56 mg/dL), or full blood glucose < 2.8 mmol/L (50 mg/dL) and which is handled by the subject himself/herself

- Or any asymptomatic plasma glucose value < 3.1 mmol/L (56 mg/dL) or full blood glucose value < 2.8 mmol/L (50 mg/dL). Minor hypoglycaemic episodes will be summarised according to this definition, and can be subject to additional analysis.

ADA hypoglycaemia classification

According to ADA the definition of a hypoglycaemic episode is categorised as:

Severe hypoglycaemia: An episode requiring assistance of another person to actively administer carbohydrate, glucagon, or other resuscitative actions.

Documented symptomatic hypoglycaemia: An episode during which typical symptoms of hypoglycaemia are accompanied by a measured plasma glucose concentration ≤ 3.9 mmol/L.

Asymptomatic hypoglycaemia: An episode not accompanied by typical symptoms of hypoglycaemia, but with a measured plasma glucose concentrations ≤ 3.9 mmol/L.

Probable symptomatic hypoglycaemia: An episode during which symptoms of hypoglycaemia are not accompanied by a plasma glucose determination (but that was presumably caused by a plasma glucose concentration ≤ 3.9 mmol/L).

Relative hypoglycaemia: An episode during which the participant reports any of the typical symptoms of hypoglycaemia and interprets those as indicative of hypoglycaemia, but with a measured plasma glucose concentration > 3.9 mmol/L.

Classification of hypoglycaemia for participants without diabetes

Participants without diabetes will not be routinely provided with blood glucose meters or diaries; hence blood glucose will not be measured in case of symptoms of hypoglycaemia unless it coincides with a clinic visit.

The hypoglycaemia events for participants without diabetes will be reported spontaneously i.e., symptoms of hypoglycaemia (not biochemically confirmed) occurring outside of visits to the clinic; severe hypoglycaemia will be defined as an episode requiring assistance of another person to actively administer carbohydrate, glucagon, or other resuscitative actions. In the event of severe or symptomatic hypoglycaemia patients will be given a glucose monitor and asked to record their blood glucose whenever they feel symptomatic.

13 Appendix 6: IPAQ scoring system

Further details including data processing rules can be found here:

<https://sites.google.com/site/theipaq/scoring-protocol>

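### The overall hypoglycaemia rate by the Novo Nordisk definition omits symptomatic severe episodes in people with diabetes but counts them in people without diabetes

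*SAP*

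**What the plan says.** SAP 2.2.1 lists three hypoglycaemia rates at 52 and 104 weeks: an overall rate by the ADA definition, an overall rate by the Novo Nordisk definition, and a severe rate. For the Novo Nordisk row, events in participants without diabetes follow the Appendix 5 text for that group, and events in participants with diabetes are taken "as per the Novo Nordisk definition in Appendix 5 for people with diabetes". The calculation is then: "Hypoglycaemia rate will be calculated per participant as total number of hypoglycaemia events divided by the total follow-up time".

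SAP Appendix 5 introduces the Novo Nordisk definition by saying that "Novo Nordisk has used this cut-off value to define minor hypoglycaemia". Two kinds of episode qualify. The first has symptoms, is confirmed by plasma glucose below 3.1 mmol/L (or full blood glucose below 2.8 mmol/L), "and which is handled by the subject himself/herself". The second begins "Or any asymptomatic plasma glucose value" and uses the same cut-offs. Protocol 10.4.2 has the same definition.

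Severe episodes are defined elsewhere in Appendix 5. The ADA classification includes them as "An episode requiring assistance of another person to actively administer carbohydrate, glucagon, or other resuscitative actions". For participants without diabetes, "severe hypoglycaemia will be defined as an episode requiring assistance of another person". The severe rate in SAP 2.2.1 is "Calculated per participant as total number of severe hypoglycaemia events divided by the total follow-up time", with no restriction by diabetes status.

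**The concern.** A rate labelled overall would normally contain the severe episodes. Here, for one patient group and one of the two definitions, it is built from a definition written for minor episodes. Protocol 6.4.2 lists an overall rate and a severe rate without saying that the overall rate is limited to minor episodes. SAP 5.8, which lists departures from the protocol, does not mention such a limit either.

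What is at stake is how one safety row is read. SAP Section 6 tabulates hypoglycaemia by glycaemic status separately for each definition. If the Novo Nordisk table follows the same event rules, its diabetes and non-diabetes lines will count different things. Appendix 5 treats severe episodes as events of special interest. Protocol 14.10.1 notes that participants with diabetes on sulphonylureas may be at higher risk of hypoglycaemia, and they belong to the group in which this row drops those events.

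**Working it through.** The plan states no figure to reproduce. The check is whether each type of episode enters each rate as written (SAP 2.2.1 read with Appendix 5).

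| Episode | Novo Nordisk overall, diabetes | Novo Nordisk overall, no diabetes | ADA overall, diabetes | Severe rate, all |
|---|---|---|---|---|
| Symptomatic, plasma glucose below 3.1 mmol/L, self-handled | counts | counts (as reported symptoms) | counts | no |
| Asymptomatic, plasma glucose below 3.1 mmol/L | counts | glucose not routinely measured | counts | no |
| Symptomatic, assistance needed | **does not count** | counts | counts | counts |

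The third row, step by step, for a participant with diabetes:

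1. The first limb of the Novo Nordisk definition requires self-handling. An assisted episode fails it at any glucose value.
2. The second limb requires no symptoms. A symptomatic episode fails it at any glucose value.
3. SAP 2.2.1 adds no further category to this row, so the episode contributes 0 to the numerator.

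The only way in is an assisted episode recorded as an asymptomatic low value, which does not close the gap.

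For a participant with M minor episodes, S symptomatic severe episodes and follow-up T years:

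- rate as written = M / T
- rate with severe included = (M + S) / T
- relative shortfall = S / (M + S)

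The shortfall runs from 0 when there are no severe episodes to 1 when all episodes are severe. Two illustrations, with assumed counts that are not from the documents and T = 1 year:

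- M = 2, S = 1: as written 2/1 = 2.0 per year; with severe included (2 + 1)/1 = 3.0 per year.
- M = 0, S = 1: as written 0/1 = 0 per year; the separate severe rate is 1/1 = 1.0 per year. The severe component exceeds the rate called overall.

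The same single severe episode in a participant without diabetes gives a Novo Nordisk overall rate of 1/1 = 1.0 per year.

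**The case against.** The strongest reply is that severe episodes are well covered elsewhere. They have their own rate in SAP 2.2.1 with rows in template 16.13, and they enter the ADA overall rate. An adverse event form is required for every hypoglycaemic episode, and SAP Section 6 lists all AEs and SAEs individually. This stands. A reader might infer that severe episodes go unreported in people with diabetes, or that an arm with more of them would look no worse. The documents do not support either inference: the excess would show in the severe rate and in the ADA overall rate, and would be missing only from the Novo Nordisk row.

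A second reply is that overall may mean across all participants, not across all severities. Template 16.13 does label one row as an overall severe event rate, and both documents say that minor episodes will be summarised by the Novo Nordisk definition. This makes a labelling fault a fair reading. It does not rescue the row, because severe episodes would still count in it for people without diabetes.

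A third reply is that the documents intend different definitions for people with and without diabetes. That is so, and it accounts for the different glucose requirements. It gives no reason to count severe episodes in one group only.

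Finally, few events may be affected. Protocol 14.10.1 regards hypoglycaemia as low risk with this drug, Protocol 7.3 excludes people currently on insulin, and Protocol 8.10 describes the number of participants with diabetes as small. Safety outcomes are summarised descriptively, and no stated decision rule uses this rate. These points limit the consequence but leave the definition as it is.

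**Conclusion.** The concern holds in a narrow form. Read literally, the Novo Nordisk overall rate excludes symptomatic severe episodes in participants with diabetes, includes severe episodes in participants without diabetes, and can fall below the severe rate for the same person. This is an inconsistency in the rule itself, so analysts following it exactly would produce an incoherent row.

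The effect is limited to one descriptive safety endpoint at two time points. The primary outcome and the other hypoglycaemia rates are untouched. The documents give no counts of minor or severe episodes, so no percentage understatement can be given. The conclusion assumes only that the Novo Nordisk definition in Appendix 5 is applied as worded, without an unwritten convention that adds severe episodes.

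**What to change.** Preferred: state in SAP 2.2.1 that, for participants with diabetes, the Novo Nordisk overall rate is the number of minor episodes (Appendix 5, Novo Nordisk definition) plus the number of severe episodes, divided by follow-up time. Count each episode once, so that an assisted episode that also meets the asymptomatic limb is not counted twice. Show the minor and severe components under the overall rate in template 16.13. Leave the Novo Nordisk definition of a minor episode unchanged, so that Appendix 5 still matches Protocol 10.4.2.

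Alternative: rename the row in SAP 2.2.1 and template 16.13 as the minor hypoglycaemia rate, and state that severe episodes are excluded from it in people without diabetes as well.

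Either option costs a sentence and a table edit. No new data collection is apparent: an episode form is already required for every episode, and the separate severe rate already requires severe episodes to be identified. The fields of the form are not shown in the documents, so the study team should confirm that minor and severe episodes can be told apart. The SAP copy is marked as a draft, and its introduction says that it will be finalised before database lock, which is the time to make the change.
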